4.8 OTHER ANALYSES

4.8.1 PK analysis

Pharmacokinetic (PK) of rilzabrutinib (PRN1008) and its metabolites , if available, will be descriptively summarized by scheduled visit and nominal sampling timepoint in the PK population. Individual PK data will be listed. The mean concentration of all three metabolites will be plotted against sampling times. Samples outside of window may be excluded from the summary as determined by PK scientist.

For PRN1008 and _____, all concentration values below the lower limit of quantitation (LLOQ) will be treated as zero in all summary statistics excepted for the geometric mean and associated coefficient of variation for which they will be considered as missing. Fo _____ all concentrations below LLOQ will be treated as LLOQ/2, given it is an endogenous compound.

Plasma rilzabrutinib concentration data might be used for population PK modeling if considered necessary and the results of population PK modeling will be reported separately from the study report.

Exploratory PK/PD analyses will be performed by PK group as deemed necessary to evaluate the expose-response relationships.

4.8.2 BTK occupancy analysis

Bruton tyrosine kinase (BTK) occupancy data will be descriptively summarized by scheduled visit and nominal sampling timepoint. Individual BTK occupancy data will be listed. Mean BTK occupancy will be plotted against sampling times.

4.8.3 Quality of life analyses

The ITP Bleeding Scale (IBLS), Immune Thrombocytopenic Purpura Patient Assessment Questionnaire (ITP-PAQ), EuroQoL-5 Dimension 5 Level (EQ-5D-5L) are administered in this study. For continuous variables, the overall score and its change from baseline will be analyzed descriptively for each time point.

IBLS

IBLS comprises of 11 sites for female and 10 sites for male, and each site is scored from 0 (none) to 2 (marked bleeding). A copy of the IBLS assessment form is provided in Section 5.5. The IBLS bleeding scales were assessed at each visit for each participant.

For each participant, an IBLS score at each visit will be calculated by taking the average across 11 items (10 for male and postmenopausal women) at 9 anatomical sites (8 for male and postmenopausal women). For each patient, a mean IBLS score will also be calculated by taking the average across all post-baseline visits during the 24-week main treatment period. Frequency and severity of bleeding according to IBLS will be summarized at each visit. The IBLS score as

28-Nov-2022 Version number: 1

defined above will be descriptively summarized at each visit. Mean IBLS score will also be descriptively summarized.

EQ-5D-5L

EQ-5D-5L is a standardized health-related quality of life questionnaire that provides a simple, generic measure of health for clinical and economic appraisal. EQ-5D consists of 2 parts – a 5-dimension descriptive system and the EQ visual analogue scale. A copy of the questionnaire is provided in Section 5.6.

The descriptive system contains 5 categories: mobility, self-care, usual activities, pain/discomfort, and anxiety/depression. Each dimension has 5 levels: no problems, slight problems, moderate problems, severe problems, and extreme problems. The number and percentage of subjects in each response category will be tabulated. Percentages are based on the number of subjects for whom an assessment is provided at the respective visit.

The EQ visual analogue scale (VAS) is a visual scale from 0–100 to record a respondent's overall self-rated health state. The respondent is asked to mark an "X" on the scale then record the corresponding number; 0 refers to the worst possible health state, 100 refers to the best possible health state. The EQ visual analogue scale will be summarized for the observed response and change from baseline.

ITP-PAQ

ITP-PAQ is a 44-item ITP-specific Patient Assessment Questionnaire. A copy of the questionnaire is attached in Section 5.7. The content of ITP-PAQ can be described as follows:

- 44 questions, rated on a Likert-type scale containing 4–7 responses (recall period: past 4 weeks)
- 10 scales for females and 9 scales for males are covered: Symptoms (6 items, items 1 to 6), Fatigue (4 items, items 7 to 10), Bother-Physical Health (3 items, items 11 to 13), Activity (2 items, items 14 to 15), Psychological Health (5 items, items 16 to 20), Fear (5 items, items 21 to 25), Overall QoL (5 items, items 26 to 30), Social Activity (4 items, items 31 to 34), Women's Reproductive Health (6 items, items 35 to 40), Work (4 items, items 41 to 44)

The ITP-PAQ scores that are used for analysis for an individual participant is obtained as follows:

• Each item/questionnaire rated on a Likert-type scale containing 4–7 responses will be transformed from 0 to 100 continuum with higher score indicating better health status, below describes the transformed score for each response category:

The transformed score for each response category equals to 100×(possible maximal item score - item score)/range, item score is recorded as PAQ_STD in the EDC database where higher score corresponds to higher frequency while lower score indicates low frequency.

For example, for an item with 5 responses, the categories contained in the item, the item score (as recorded in EDC), and the transformed score are listed below:

Property of the Sanofi group - strictly confidential

Page 26

	Item score (PAQ_STD in EDC)	Transformed score
Category		
All the time	5	0
Most of the time	4	25 (100×1/4)
Some of the time	3	50 (100×2/4)
Rarely	2	75 (100×3/4)
Never	1	100 (100×4/4)

Each item checked (i.e., non-missing) will generate a numerical score ranging from 0 to 100

- The scale score is obtained by taking the arithmetic mean of its associated items. For example, symptoms score will be obtained by averaging its associated 6 item scores, ranging from 0 to 100, with higher scores indicating better health status
- Each female and male participants will have 10 scale scores and 9 scale scores respectively per visit where ITP-PAQ is performed

In the computation of scale scores, missing data on a particular scale will be imputed if $\geq 50\%$ of the items in that scale is non-missing. Such missing values will be imputed using the mean of the non-missing items. If there are more than 50% of missing data, the scale score is considered as missing.

ITP-PAQ will be summarized for the observed response and change from baseline by scale and by visit. Graphic presentation may be provided as needed.

4.9 INTERIM ANALYSES

No interim analysis is planned for this study.

5 SUPPORTING DOCUMENTATION

5.1 APPENDIX 1 LIST OF ABBREVIATIONS

ALP: Alkaline phosphatase ALT: Alanine aminotransferase

aPTT: activated partial thromboplastin time

AST: Aspartate aminotransferase

ATC: anatomic category
BTK: Bruton tyrosine kinase
BUN: Blood Urea Nitrogen
CPK: Creatinine phosphokinase

CS: corticosteroid
DBL: data base lock
ECG: electrocardiogram

EQ-5D-5L: EuroQoL-5 Dimension 5 Level

HLGT: high-level group term HLT: high-level term

IMP: investigational medicinal productINR: International Normalized RatioITP: immune thrombocytopeniaITP-BAT: ITP Bleeding Assessment Tool

ITP-PAQ: Idiopathic Thrombocytopenic Purpura Patient Assessment

ITT: intent-to-treat
LLT: lower-level term
LTE: long-term extension

NCI-CTCAE: National cancer institute common terminology for adverse events

NPV: Negative predictive value, negative predictive value

PCSA: potentially clinically significant abnormality

PK: Pharmacokinetic

PPV: positive predictive value

PT: preferred term

SAP: statistical analysis plan SOC: system organ class

TE: treatment-emergent, treatment-emergent

TEAE: treatment-emergent adverse event TPO-RA: thrombopoietin receptor agonist

WHO-DD: World Health Organization-drug dictionary

5.2 APPENDIX 2 DEMOGRAPHICS AND BASELINE CHARACTERISTICS, PRIOR OR CONCOMITANT MEDICATIONS

Demographics, baseline characteristics, ITP history, medical history

The following demographics and baseline characteristics, ITP history, medical history will be summarized using descriptive statistics in the enrolled population.

Demographic and baseline characteristics

- age in years as quantitative variable and in categories ($<65, \ge 65$)
- gender (Male, Female)
- race (White, Black or African American, Asian, American Indian or Alaska native, native Hawaiian or other pacific islander, Other)
- ethnicity (Hispanic or Latino, not Hispanic or Latino)
- weight (kg) at screening
- body mass index (BMI) (kg/m²) at screening

Baseline safety and efficacy parameters (apart from those listed above) will be presented along with the safety and efficacy summaries.

ITP history

- type of ITP: primary vs secondary
- duration of ITP: persistent vs chronic, the definition of which is the same as Section 4.3.5
- duration of ITP (primary or secondary) (years), where:
 - duration of ITP (years) = ((Date of first study drug dosing Date participant was diagnosed with ITP+ 1)/30.4)/12
- average of two qualified screening platelet counts as collected in eCRF
- baseline platelet count, as defined in Section 4.1
- baseline platelet count: <15,000/μL vs. ≥15,000/μL
- splenectomy (Y/N)

Medical and surgical history will be coded to a PT and associated primary SOC using the MedDRA currently in effect at Sanofi at the time of database lock.

Prior or concomitant medications

All medications will be coded using the World Health Organization-Drug Dictionary (WHO-DD) using the version currently in effect at Sanofi at the time of database lock.

- Prior medications are those the participant used prior to first IMP intake. Prior medications
 can be discontinued before first administration of IMP or can be ongoing during treatment
 period.
- Concomitant medications are any interventions received by the participant concomitantly to the IMP during the on-treatment period (from the first administration of IMP to the last IMP intake + 1).
- Post-treatment medications are those the participant took in the period running from the end of the concomitant medications period up to the end of the study.
- A given medication can be classified as a prior medication and/or as a concomitant medication and/or as post-treatment medication. If it cannot be determined whether a given medication was taken prior or concomitantly or post, it will be considered as prior, concomitant, and post-treatment medication.

The prior, concomitant, and post-treatment non-ITP medications will be summarized for the ITT population, by anatomic and therapeutic level. The summaries will be sorted by decreasing frequency of anatomic category (ATC). Therapeutic classes are sorted by decreasing frequency within each anatomic class. In case of equal frequency, alphabetical order will be used. Participants will be counted once in each ATC category (anatomic or therapeutic) linked to the medication.

Prior ITP, concomitant non-rescue ITP, and concomitant rescue ITP therapies/medications will be summarized separately by the ATC level 4 chemical class and medication name.

The following prior ITP therapies will be presented:

- number of prior unique ITP therapies identified using standardized medication name
 - counting splenectomy as an ITP therapy
 - not counting splenectomy as an ITP therapy
- number of prior unique ITP therapies identified using standardized medication name and counting different corticosteroids as one therapy
 - counting splenectomy as an ITP therapy
 - not counting splenectomy as an ITP therapy
- number of prior ITP therapies, identified by eCRF entry records
- number of participants with the following ITP medications, respectively:
 - Corticosteroids
 - TPO-RA
 - IVIG

- Anti-D immunoglobulin
- Rituximab
- Fostamatinib
- Immunosuppressants and other immunomodulatory agents (including Cyclophosphamide)
- Dapsone
- Danazol
- Investigational ITP medications
- number of participants responded to prior ITP therapy including splenectomy,
 (i.e., resulted in platelet count ≥50,000/μL per eCRF) including splenectomy
- number of participants responded to 1) prior corticosteroids, 2) prior TPO-RA, 3) prior Rituximab, 4) prior IVIG or Anti-D immunoglobulin respectively.

5.3 APPENDIX 3 DATA HANDLING CONVENTIONS

Platelet count assessments

For efficacy analyses using weekly platelet counts, the use of local platelet count will be prioritized, central platelet count will be used only when local is missing; the use of scheduled visit will be prioritized, and unscheduled visit will be used when scheduled is missing. If a weekly (starting from week 2) scheduled platelet count is missing, then an unscheduled platelet count will be allocated to the corresponding visit. See Table 6 for details.

Analysis windows for time points

The following analysis windows will decide how the scheduled and/or unscheduled visits will be used in the by-visit analyses of efficacy, safety, and participant reported outcome variables.

Platelet counts conducted locally will be used for the efficacy analyses. Platelet counts conducted centrally at Clinic Visits will be used as a back-up for missed or non-analyzable local lab samples.

A scheduled measurement will be used if it is available. Otherwise, an unscheduled measurement (including early withdrawal visit) will be allocated to a scheduled visit if it is within the analysis window of the scheduled visit. After applying these time windows, if multiple assessments are associated to the same time point, the closest from the targeted study day will be used. If the difference is a tie, the value after the targeted study day will be used. If multiple valid values exist within a same day, then the first value of the day will be selected.

If there is no measurement for a given parameter in an analysis window, data will be considered missing for the corresponding visit.

28-Nov-2022 Version number: 1

Table 6 - Analyses window definition

Scheduled visit post baseline	Targeted study day (Analysis window) – Platelet count only	Targeted study day (Analysis window) – Other ^a
Week 1 to LTE Month 6		
Week n ^b	1+7*(n-1) (+/-3)	
Week 5	29 (+/-3)	29 (-13,+14)
Week 9	57 (+/-3)	57 (-13,+14)
Week 13	85 (+/-3)	85 (-13,+14)
Week 17	113 (+/-3)	113 (-13,+14)
Week 21	141 (+/-3)	141 (-13,+14)
Week 25/ C1D1_LTE	169 (+/-3)	169 (-13,+14)
C1D8_LTE	176 (+/-3)	
C1D15_LTE	183 (+/-3)	
C1D22_LTE	190 (+/-3)	
C2D1_LTE	197 (+/-3)	197 (-13,+14)
C2D8_LTE	204 (+/-3)	
C2D15_LTE	211 (+/-3)	
C2D22_LTE	218 (+/-3)	
C3D1_LTE	225 (+/-3)	225 (-13,+14)
C3D8_LTE	232 (+/-3)	
C3D15_LTE	239 (+/-3)	
C3D22_LTE	246 (+/-3)	
C4D1_LTE	253 (+/-3)	253 (-13,+14)
C4D8_LTE	260 (+/-3)	
C4D15_LTE	267 (+/-3)	
C4D22_LTE	274 (+/-3)	
C5D1_LTE	281 (+/-3)	281 (-13,+14)
C5D8_LTE	288 (+/-3)	
C5D15_LTE	295 (+/-3)	
C5D22_LTE	302 (+/-3)	
C6D1_LTE	309 (+/-3)	309 (-13,+14)
C6D8_LTE	316 (+/-3)	
C6D15_LTE	323 (+/-3)	
C6D22_LTE	330 (+/-3)	

Scheduled visit post baseline	Targeted study day (Analysis window) – Platelet count only	Targeted study day (Analysis window) – Other ^a
LTE Month 7 afterwards		
C7D1_LTE	337 (-3,+14)	337 (-13,+14)
C8D1_LTE	365 (-13,+14)	365 (-13,+14)
C9D1_LTE	393 (-13,+14)	393 (-13,+14)
C10D1_LTE	421 (-13,+14)	421 (-13,+14)
C11D1_LTE	449 (-13,+14)	449 (-13,+14)
C12D1_LTE	477 (-13,+14)	477 (-13,+14)
Q1_LTE	505 (-13,+42)	505 (-13,+42)
QX_LTE where X=2,3,	505+28*3*(X-1) for X=2,3, (-41,+42)	505+28*3*(X-1) for X=2,3, (-41,+42)

Study days are calculated considering Day 1 as the day of first administration of intervention.

Unscheduled visits

Unscheduled visit measurements of laboratory data, vital signs, ECG and QOL data will be used for computation of baseline, the last on-treatment value, analysis according to PCSAs, and the shift summaries for safety whenever applicable. They will also be included in the by-visit summaries if they are re-allocated to scheduled visits.

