### Part B:

After a screening period of up to 4 weeks, patients will receive rilzabrutinib treatment for up to 24 weeks, starting on Study Day 1. All patients will complete 4 weeks of post-treatment safety follow-up.

The expected study duration is approximately 28 months from the first patient treated to last patient completing. Study duration for individual patient is approximately 32 weeks.

The duration of the LTE will be determined by the rules outlined in Section 4.6.

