# 16.4 Appendix 4: Schedule of Assessments (Part B)

			Activ	ve Treatment Po	eriod for 24 We	eks and 4 Weel	k Follow Up Pe	eriod 			
	Screening (D-28 to D-1)	Enrolment Week 1 SD1	Week 5 SD29	Week 9 SD57	Week 13 SD85	Week 17 SD113	Week 21 SD141	Last Day of Treatment Week 25 SD169	End of Study SD197 / 4 weeks post last dose	Weekly Lab Visits Between Clinic Visits	Early Withdrawal/ Unscheduled visit
Informed Consent	X										
Inclusion/Exclusion Criteria	X	X1									
AEs	X	X	X	X	X	X	X	X	X		X
Concomitant Medications	X	X	X	X	X	X	X	X	X		X
Height	X										
Weight	X	X	X	X	X	X	X	X	X		X
Physical exam/med history 	X	X	X	X	X	X	X	X	X		X
ECG (12-lead, single)	X	X	X	X	X	X	X	X	X		X
Vital Signs	X	X	X	X	X	X	X	X	X		X
Urinalysis	X	X	X	X	X	X	X	X	X		X
Hep B & C, HIV 	X										
Pregnancy test 	X	X	X	X	X	X	X	X	X		X
FSH 	X										
ABO and Rh Blood Type 	X										
Serum Chemistry	X	X	X	X	X	X	X	X	X		X
Hematology, differential, reticulocytes	X	X	X	X	X	X	X	X	X	X	X
PT/INR PTT	X	X	X	X	X	X	X	X	X		
TPO levels	1	X	X	X	X	X	X	X	X		
Hemolysis panel 	1	X	X	X	X	X	X	X	X		
Mean platelet volume 		X	X	X	X	X	X	X	X		
Immature platelet fraction 				12							
1					·						
BTK Occupancy 		X	X	X				X			
PK sample 		X	X	X							

			Active Treatment Period for 24 Weeks and 4 Week Follow Up Period 								
	Screening (D-28 to D-1)	Enrolment Week 1 SD1	Week 5 SD29	Week 9 SD57	Week 13 SD85	Week 17 SD113	Week 21 SD141	Last Day of Treatment Week 25 SD169	End of Study SD197 / 4 weeks post last dose	Weekly Lab Visits Between Clinic Visits 1	Early Withdrawal/ Unscheduled visit
QOL Questionnaires 	X	X	X	X	X	X	X	X	X		
IBLS	X	X	X	X	X	X	X	X	X		X

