4.3.2 Main analytical approach

The responder of the primary endpoint must have met ALL of the following criteria:

 Platelet counts ≥ 50,000/µL for at least 8 out of the last 12 weeks [Week 14 (Day 92) to Week 25 (Day 169)] during the 24-week treatment period (or equivalently the ontreatment period for efficacy).

The on-treatment period for efficacy is defined as the period from the date of the 1st IMP administration

- up to 1 day after the last IMP administration for participants who did not enter LTE, or
- Week 25 (Day 169) visit for participants who entered LTE.

The on-treatment period for efficacy will be used for all efficacy analyses related to platelet counts.

And,

- Not rescued after 10 weeks of treatment. "Rescued after 10 weeks of treatment" for efficacy analysis is defined as from Week 11 (Day 71) to the day prior to the last date of IMP administration for those do not enter LTE or the visit date of Week 25/C1D1_LTE (Day 169) for those entered LTE.
- Not discontinued before Week 25 due to related TEAE (per investigator's assessment), lack of response, or need to rescue medication as recorded in eCRF, i.e., participants who discontinue before Week 25 and the discontinuation reasons are treatment related adverse event (AE), lack of response, or need of rescue medication will be considered as non-responders.

The response rate will be summarized for ITT population along with the 95% exact Clopper-Pearson Confidence Interval (CI).

Platelet counts and the change from baseline will be summarized by visit. The time course of platelet count will be described graphically, and the following plots will also be provided:

- Individual platelet count profile: line plot of platelet count by visit for each participant
- Spaghetti plot platelet count by participant in each study period (i.e., main and LTE)
- Median platelet count/change from baseline by visit in each study period

Property of the Sanofi group - strictly confidential

28-Nov-2022 Version number: 1

An unscheduled platelet count will be allocated to a scheduled visit if it is within the visit window of the scheduled visit where a platelet count is not available (see Section 5.3).

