4.7.1 Extent of exposure

The extent of IMP exposure will be assessed by the duration of IMP exposure and treatment compliance and summarized within the safety population. Duration of study drug exposure (days) and treatment compliance will be summarized for main 24-week treatment period and LTE treatment period, respectively.

Duration of IMP exposure

Duration of IMP exposure will be summarized based on treatment periods, which are defined below:

• Duration of study drug exposure in each treatment period (days) = (last IMP administration date during main or LTE treatment period - first IMP administration date in each treatment period) + 1, regardless of unplanned intermittent interruption.

Last dose date can be found in eCRF. If the date of the last dose of IMP is missing, the duration of IMP will be left as missing. In cases where participants are still on-going in LTE when the data base lock (DBL) occurred, the data cut-off date (last participant last visit date in 24-week treatment period) will be used as the last dose date of LTE.

Duration of IMP exposure will be summarized quantitatively and categorically by month: 1 to 28 days (Week 1 to Week 4), 29 to 56 days (Week 5 to Week 8), ..., 141 to 168 (Week 21 to Week 25), 169 to 196 days (Month 1 LTE), 197 to 224 days (Month 2 LTE) etc.

Additionally, the cumulative duration of treatment exposure (expressed in participant-months) will be provided.

Treatment compliance

A given administration will be considered noncompliant if the participant has dates indicating missing doses as recorded in eCRF.

Percentage of treatment compliance for a participant will be defined as the number of administration days that the participant was compliant divided by the total number of administration days (i.e., Duration of IMP) ×100%, during main 24-week treatment period and LTE treatment period, respectively.

28-Nov-2022 Version number: 1

Treatment compliance will be summarized quantitatively and categorically: < 80%, 80% to 100%, and >100%.

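### SAP Part B has no follow-up row or on-drug limit for by-visit laboratory, vital-sign, ECG, EQ-5D-5L and ITP-PAQ summaries, and its exposure classes label some participants who never entered the LTE as LTE

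*SAP*

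**What the plan says.** Visit assignment in Part B is governed by SAP Part B section 5.3: "The following analysis windows will decide how the scheduled and/or unscheduled visits will be used in the by-visit analyses of efficacy, safety" and participant-reported outcomes. A scheduled value is used if there is one; otherwise "an unscheduled measurement (including early withdrawal visit) will be allocated to a scheduled visit if it is within the analysis window" of that visit. Table 6 then lists windows by study day from first dose. It goes from Week 25/C1D1_LTE (Day 169) straight to C2D1_LTE (Day 197) and later LTE visits. It has no row for post-treatment follow-up.

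The protocol's Part B schedule (Appendix 4) does have such a visit: "End of Study SD197 / 4 weeks post last dose". Laboratory tests, vital signs, ECG, IBLS and quality-of-life questionnaires are all marked there.

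Some analyses carry a period limit. SAP 4.3.2 says: "The on-treatment period for efficacy will be used for all efficacy analyses related to platelet counts". That period ends one day after last IMP for those who do not enter the LTE. SAP 4.4.2 confines the secondary endpoints, IBLS change among them, to the 24-week treatment period, and 4.8.3 does the same for the mean IBLS score. In 4.7.3.1 the laboratory, vital-sign and ECG statistics are given for each planned visit, and only the last value is tied to the on-treatment period. For EQ-5D-5L and ITP-PAQ, 4.8.3 states no period.

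On exposure, SAP 4.7.1 defines duration within each period as the last minus the "first IMP administration date in each treatment period) + 1, regardless of unplanned intermittent interruption". The classes include "141 to 168 (Week 21 to Week 25), 169 to 196 days (Month 1 LTE"). Protocol Appendix 4 labels its final treatment column "Last Day of Treatment Week 25 SD169".

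**The concern.** A table headed by a treatment or LTE visit will be read as describing people on drug at that visit. If values taken after stopping are placed by study day alone, a main-period row can mix on-drug values with values from people who have stopped, and the C2D1_LTE row can mix LTE participants with completers who did not enter the LTE. The groups differ, because LTE entry requires a platelet response (Protocol 4.2). With about 23 participants, a few such values could shift a visit mean.

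The exposure classes raise a related question. The class labelled as ending at Week 25 stops a day before the day on which both Table 6 and the protocol place Week 25, and the next class is labelled LTE.

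**Working it through.** **Inputs.** Table 6: target days, and the non-platelet window of −13/+14 days. Protocol Appendix 4: last treatment day SD169; End of Study at SD197 or 4 weeks after last dose. SAP 4.7.1: duration formula and classes.

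**The plan's own figure.** Table 6 gives the Week n target as 1 + 7 × (n − 1). For n = 25 this is 1 + 7 × 24 = 169, which agrees with Table 6 and with SD169 in the protocol.

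**Windows and follow-up day.** Each non-platelet window is target − 13 to target + 14. The follow-up day is L + 28, where L is the day of last dose.

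| Table 6 row | Target | Window | L for which L + 28 falls here |
|---|---|---|---|
| Week 5 | 29 | 16–43 | 1–15 |
| Week 9 | 57 | 44–71 | 16–43 |
| Week 13 | 85 | 72–99 | 44–71 |
| Week 17 | 113 | 100–127 | 72–99 |
| Week 21 | 141 | 128–155 | 100–127 |
| Week 25/C1D1_LTE | 169 | 156–183 | 128–155 |
| C2D1_LTE | 197 | 184–211 | 156–183 |

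Each window starts the day after the previous one ends, with no gap or overlap (checked from Day 16 to Day 323). So by study day no 4-week follow-up value can fall outside a treatment or LTE row:

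- Last dose Day 60: 60 + 28 = 88, inside Week 13 (72–99).
- Last dose Day 169: 169 + 28 = 197, exactly the C2D1_LTE target.

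The preference for scheduled values does not prevent this. Someone who stopped on Day 60 has no on-drug Week 13 value, and a completer outside the LTE has no C2D1_LTE visit.

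**Exposure.** With first dose on Day 1, main-period duration is L − 1 + 1 = L days.

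- L = 168: 168 days, class 141–168 (main).
- L = 169: 169 days, class 169–196 (Month 1 LTE).
- If the last dose may fall within ±3 days of Day 169 (an assumption, matching the platelet window in Table 6), L = 166–168 gives the main class and L = 169–172 the LTE class.

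For an LTE entrant, SAP 4.1 ends the main period the day before the first LTE dose. With a first LTE dose on Day 169, that is 168 days. The LTE label then falls on the completer who stayed out of the LTE.

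LTE duration has the opposite mismatch. It is counted from the first LTE dose, so 20 LTE days fall in the class 1–28, labelled Week 1 to Week 4. An LTE duration would reach the Month 1 LTE class only at 169 days, after 168 / 28 = 6 full cycles.

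**The case against.** The strongest reply is that no sentence places the End of Study visit in a treatment or LTE row. The re-allocation rule concerns unscheduled and early-withdrawal measurements. End of Study is a planned visit with its own column in the protocol, and 4.7.3.1 reports by planned visit, so a programmer could give it its own label. SAP 4.1 also assigns post-treatment data of people outside the LTE to the main treatment-emergent period, so putting them under C2D1_LTE would conflict with the SAP's own periods. This stands against reading the text as a stated misallocation. It does not remove the gap: section 5.3 says the windows govern scheduled visits too, Table 6 has no row for this one, and the rule that does re-allocate values has no on-drug check. The Part A SAP (3.4.3) lists End of Study as a visit of its own; Table 6 of Part B does not.

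A reader might infer that nothing outside platelet counts is limited to treatment, so that the IBLS secondary endpoint is distorted. The documents do not support that. SAP 4.4.2 limits secondary endpoints to the 24-week treatment period, 4.3.2 equates that with the on-treatment period for efficacy, and 4.8.3 limits mean IBLS. The Day 88 IBLS value in the example is excluded.

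A reader might also try to put a figure on the mixing at C2D1_LTE. With 10 LTE entrants and 8 completers outside the LTE, 8 / (10 + 8) = 44% of values would be off drug. Both counts are assumed, and the result needs the disputed placement as well, so it is not evidence of size.

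On exposure, one can say that the class list is open-ended, that the protocol elsewhere says "patients will receive rilzabrutinib treatment for up to 24 weeks, starting on Study Day 1", and that exactly 24 weeks (168 days) is classed as main. All true. The classes might also be meant as cumulative across both periods. That would repair the LTE durations, but 4.7.1 defines duration per period, and a completer at 169 days would still carry an LTE label. Disposition counts LTE entry separately (4.2), so nobody becomes an LTE entrant there.

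**Conclusion.** The point holds in a limited form, and its severity is minor.

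- **By-visit summaries.** For laboratory, vital-sign, ECG, EQ-5D-5L and ITP-PAQ data the SAP states no on-treatment condition and offers no follow-up row. Values after last dose can fall in treatment or LTE rows: by rule for unscheduled and early-withdrawal values, and by one open reading for End of Study. Two programmers could produce different tables from the same text.
- **Exposure classes.** These are wrong as written. A completer outside the LTE with last dose on or after Day 169 is labelled Month 1 LTE, and the cumulative-day LTE classes do not match durations counted from the first LTE dose.

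The primary endpoint and the platelet analyses have their own limit. The PCSA analyses include post-treatment data by design. IBLS change and mean IBLS are limited to the 24-week period. No effect on any estimate has been shown; what is at stake is the labelling and content of descriptive tables. How many participants are affected depends on how many stop early and how many complete without entering the LTE, which the documents do not give.

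**What to change.** In SAP Part B section 5.3, apply the Table 6 treatment rows only to assessments up to last IMP + 1 day, apply the LTE rows only to LTE entrants, and report later values under a separate post-treatment follow-up row. State that the End of Study visit belongs to that row.

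In 4.7.1, use two class lists. For the main period, let the last class include Day 169 and its visit window. For the LTE, count from the first LTE dose (1–28, 29–56 days, and so on). This does not decide whether a dose is taken on Day 169; the protocol's up-to-24-weeks wording and its SD169 label differ by a day and should be reconciled.

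The cost is a few sentences in the SAP and a programming filter. The downside is slightly fewer values at some visits; follow-up data are still reported, under their own label.
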